10.1 UNC ELISpot assays

Peptides: A study-specific peptide plate (PPL039 – CM longitudinal) was made and QC'd in healthy donors prior to testing in CM participants . Stability the peptide plate was tested over the course of the study using reference PBMC. Each plate contains pools of overlapping peptides spanning i) Mosaic-1 (Mos-1) and ii) Mosaic-2 (Mos-2) immunogens designed, iii) Subpool G1 iv) Subpools G2, P4, P5 v) Subpool P3-A vi) Subpool P3-B vii) Subpool P6 viii) Clade B Env ix) Clade B Nef/Acc (Rev, Tat, Vif, Vpu, Vpr) and x) Junctions ELISpot: ELISpots were performed as previously described [2]. 200,000 PBMC were added/well.

Spot counting: Peptide plates were counted using an AID ELISpot reader. Plates were first read using standardized settings with no changes made and counts stored (see 'Count Settings Intensity 10' below). Plates were then re-read using an administrator setting allowing minor changes to spot counts such as removal of dust, as per SOP G002B_V2. Any changes between first and admin reads were documented both as print-outs and exported text files.

Data Listings: The data listing comprises one worksheet per participant. ELISpot data were directly exported as text files (after the Admin Read) from the AID reader and imported into an Excel spreadsheet. All data were reviewed by technicians, [name] and/or [name] prior to submission.

10.2 Lab QC Controls

All technicians in the [name] laboratory have passed ELISpot proficiency testing using internal QC controls. Full training records are maintained. The [name] laboratory also participates in NIH-sponsored EQUAPOL ELISpot proficiency.

All cell cultures and peptide plates are routinely screened using light microscopy for evidence of infection.

Peptide plates have been tested for stability against reference PBMC over the course of the study.

Freezers, cryostores and incubators used in these experiments have been temperaturemonitored and all key equipment such as biosafety hoods, cell counter and AID reader maintained under service contract.

- Only data that meets laboratory QC parameters will be submitted for analysis.
- Within participant, longitudinal timepoints may be performed on different days if standard QC measures (counting, controls) are met.
- If ELISpots (same visit) are repeated and results discordant, then no data will be submitted for secondary endpoint analysis.
- If ELISpots (same visits) are repeated and results concordant, then the first assay performed will be submitted for secondary endpoint analysis.
- Typically, 0.20 million PBMC/well were added. Other input values are accepted. All magnitude data will be graphed as SFU/million cells.

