e. COVID-19 Antibody Testing: COVID-19 nucleocapsid antibody testing on stored plasma as indicated per the SoA, Section 1.3.

f. Plasma/PBMC for Immunology Studies: Plasma and cryopreserved PBMC will be stored for analysis of low-level viremia, T-cell specificity, phenotype and function of immune cells, and virologic measurements per the SoA, Section 1.3. Specific testing will include the following:

- 1) Measurement of T cell responses pre- and post-treatment
- 2) Measurement of T cell virus inhibition pre- and post-treatment
- 3) Phenotyping of both total and specific CD4⁺ and CD8⁺ T cell activation, homing and memory differentiation using flow cytometry pre- and post-treatment
- 4) Functional analysis (e.g., anti-viral cytokine and lytic molecule release) of both total and specific T cells pre- and post-treatment
- 5) Low-level HIV-1 RNA assays pre- and post-treatment

NOTE: Site laboratory standardized protocols will guide the performance of all research assays.

NOTE: See Section 7.1 regarding collection of stored Plasma/PBMC for Immunology Studies for participants who discontinue ART or do not complete study treatment.

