| G1 (MOS1+MO S2) | PP076 | 18mer peptides overlapping (64) by 11aa spanning G1 of both Mosaic-1 and Mosaic-2 | 2ug/ml | 4 | Examining breadth at the subpool level. Also, a second an independent check of Mos-1/Mos-2 data. Specifically, we expect any changes in Mos-1- or Mos-2-specific T cell responses to be reflected in changes at the sub-pool level. | Secondary: Breadth (0-5) |
| G2_P4 P5 (MOS1+MO S2) | PP077 | 18mer peptides overlapping (38) by 11aa spanning G2, P4 and P5 of both Mosaic-1 and Mosaic-2 | 2ug/ml | 4 | Examining breadth at the subpool level. Also, a second an independent check of Mos-1/Mos-2 data. | Secondary: Breadth (0-5) |
| P3-A (MOS1+MO S2) | PP078 | 18mer peptides overlapping (42) by 11aa spanning the 5` half of P3 of both Mosaic-1 and Mosaci-2 | 2ug/ml | 4 | Examining breadth at the subpool level. Also, a second an independent check of Mos-1/Mos-2 data. | Secondary: Breadth (0-5) |

| P3-B (MOS1+MO S2) | PP079 | 18mer peptides overlapping (54) by 11aa spanning the 5` half of P3 of both Mosaic-1 and Mosaic-2 | 2ug/ml | 4 | Examining breadth at the subpool level. Also, a second an independent check of Mos-1/Mos-2 data. | Secondary: Breadth (0-5) |
|-------------------------|----------------|--|--------|---|--|--|
| P6 (MOS1+MO S2) | PP080 | 18mer peptides overlapping (41) by 11aa spanning the 5` half of P3 of both Mosaic-1 and Mosaic-2 | 2ug/ml | 4 | Examining breadth at the subpool level. Also, a second an independent check of Mos-1/Mos-2 data. | Secondary: Breadth (0-5) |
| Clade B Env | PP004 | Overlapping 18mer peptides spanning Clade B Envelope (year) | 2ug/ml | 4 | Not in vaccines. i) Descriptive analysis of whether vaccination has any nonspecific effects on ENV-specific T cell responses in ELISpot ii) Immunodominance analysis | Exploratory: (SFU/10^6 PBMC) |
| Clade B Nef/Acc | PP081 | Overlapping peptides spanning Nef, Rev, Tat, Vif, Vpr, Vpu | 2ug/ml | 4 | Not in vaccines. i) Descriptive analysis of whether vaccination has any nonspecific effects on ENV-specific T cell responses in ELISpot ii) Immunodominance analysis | Exploratory: (SFU/10^6 PBMC) |
| Junctions | PP082 B | Overlapping peptides spanning junctional sequences between the 6 HIV regions of the vaccine immunogens across the four immunogens inC1, C62, M3,M4 | 2ug/ml | 4 | In the vaccine immunogen, but not HIV-specific. Descriptive analysis as to whether vaccination induced T cell response to these regions | Exploratory: (SFU/10^6 PBMC) |

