4.1.8 Test Size and Confidence Levels

For all primary and secondary endpoints in this trial, 95% confidence intervals will be computed for all relevant estimates. Because this is a Phase I study with a small sample size and exploratory endpoints, results will be presented without adjustment for multiple comparisons or multiple testing of endpoints. Given the small sample size, exact methods that do not rely on large sample assumptions will be used for statistical inference and will always be presented with corresponding descriptive statistics and/or data visualization. Type-I error control (alpha) for all comparisons will be set to 0.05, and all tests will be two-sided.

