Design: Empirical power calculated by simulating 10,000 random samples, assuming log-transformed HIV-specific T-cell response follows a normal distribution. The effect under the alternative hypothesis was a GMR of 2 on the raw T-cell response measures. An SD of 0.8 for both pre- and post-vaccination measurements was assumed to calculate power. This assumption was based on previous, log-transformed HIV-specific T-cell response data, which gave a between-participant SD of 0.8 at baseline. A within-participant Pearson correlation of between r = 0.8 and r = 0.9 was assumed between paired log-transformed HIV-specific T-cell response measures.

Design: Empirical power calculated by simulating 10,000 random samples from a normal distribution. Assume a p=90% or p=87% probability that the difference in HIV-specific T-cell response for any given participant in the **C1C62-M3M4** arm is higher than any given individual in the **C62-M4** arm.

Statistical Test for Power: Two-Sided Exact Wilcoxon Signed-Rank Test to achieve exact p-value < 0.05

Statistical Test for Power: Two-Sided Exact Wilcoxon Rank-Sum Test to achieve exact p-value < 0.05

| Sample Size: N=8 (per arm) | Sample Size: N=8 (per arm) |
|----------------------------------|----------------------------|
| Empirical Power: | Empirical Power: |
| >95% (within-individual r = 0.9) | 90% (p=90% effect size) |
| >80% (within-individual r = 0.8) | >80% (p=87% effect size) |

Table 5: Power for detecting differences in T-cell breadth between arms.

Aim: Determine the statistical power necessary to detect a change in T-cell breadth (T cell breadth is defined as the number of reactive HIV subpools as described in Section 8.2) between vaccine arms

Data: For the C62-M4 and C1C62-M3M4 arms, we anticipate that vaccination will induce a change of breadth (the detection of a new reactive T cell epitope) ranging from 0-3 epitopes and 2-6 epitopes, respectively. We anticipate that C62-M4 will induce a change in breadth with the following frequency distribution: 0 (20% of participants), 1 (50%), 2 (20%), and 3 (10%). We anticipate that C1C62-M3M4 will induce a change in breadth with the following frequency distribution: 2 (30% of participants), 3 (40%), 4 (15%), 5 (10%), and 6 (5%). Note, that these estimates are based on previous empirical

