 - i. Report results as log2 fold change to each antigen pool (Mos-1/PP062, Mos-2/PP063, Subpools PP076-080) for each vaccine arm.
 - ii. All log2 fold changes will be statistically assessed using a two-sided exact Wilcoxon signed-rank test. If a value in the dataset matches the hypothetical value, then the value will be ignored in the analysis (Wilcoxon method of handling ties).
 - c. Secondary analyses between vaccine arms (n=8/group):
 - i. Examine the between-arm difference in log2 fold change to each antigen pool Mos-1/PP062 and Mos-2/PP063 pre- and post-vaccination.
 - ii. Between-arm comparisons in log2 fold changes will be statistically assessed using a two-sided exact Wilcoxon rank-sum test. If a value in the

dataset matches the hypothetical value, then the value will be ignored in the analysis (Wilcoxon method of handling ties).

C. Calculate gain or loss of a positive T cell responses to vaccine immunogens to assess breadth (Outcome 2 T-Cell Breadth):

- a. To analyze breadth, we are looking at the number of reactive subpools before (screening, enrollment, Day 0) and after vaccination (Day 56).
- b. As per section 8.3.A.b, assess whether ex vivo T cell response is reactive/positive at each visit.

c. Analysis criteria:

- i. For breadth analysis, output should be binary: non-response or response
- ii. No. of positive HIV subpools 1-5 (PP076-PP080) pre-vaccination at baseline.
- iii. Pre-vaccination breadth: if a reactive/positive T cell response is observed at *any* pre-vaccination visit that the participant will be deemed to have a positive/reactive T cell response pre-vaccination.
- iv. No. of positive antigen subpools 1-5 (PP076-PP080) post-vaccination.
 - Post vaccination breadth: ex vivo vaccine-induced T cell response must be detected at > 1 post-vaccination visit, Day 35 onward.
- v. Data was only submitted for analysis if it met biological criteria.
- d. Secondary analysis across all vaccinees (n=16) & within arm (n=8/group):
 - i. Change in number of positive HIV subpools (PP076-80) at Day 56 (post-vaccination) vs baseline (pre-vaccination) across all vaccinees (n=16).
 - ii. Change in number of positive/reactive HIV subpools (PP076-80) at Day 56 (post-vaccination) vs baseline (pre-vaccination) for each vaccine arm.
 - iii. The change in number of positive/reactive antigen subpools will be statistically assessed using a two-sided exact Wilcoxon signed-rank test. If

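### SAP 10.2 lets one participant's pre- and post-vaccination ELISpots run on different days, and the within-arm magnitude tests have nothing to remove a run shift that lines up with pre versus post

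*SAP*

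**What the plan says.** SAP 10.2 sets the assay-day rule: "Within participant, longitudinal timepoints may be performed on different days if standard QC measures (counting, controls) are met". It adds that only data passing laboratory QC are submitted. It describes reference PBMC as a check on peptide-plate stability, with no numerical limit and no use in adjusting results.

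SAP 8.2 and 8.3.B define the fold change as Day 35 or Day 42 over the average of the baseline visits, after subtracting mock wells. For the within-arm outcomes, "All log2 fold changes will be statistically assessed using a two-sided exact Wilcoxon signed-rank test". SAP section 8 plans no vaccine-versus-placebo magnitude test.

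Protocol 8.1.7.f shows that the cells are stored: "Plasma and cryopreserved PBMC will be stored for analysis of low-level viremia, T-cell specificity, phenotype and function of immune cells". SAP Table 1 also lists pools that are not in the vaccines. For Env the purpose is "Descriptive analysis of whether vaccination has any nonspecific effects on ENV-specific T cell responses in ELISpot", and the Nef/Acc row is likewise exploratory. SAP 8.3.B already calls for fold changes to non-vaccine as well as vaccine immunogens.

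**The concern.** A within-arm test attributes any consistent rise from baseline to vaccination. If a participant's baseline and post-boost samples are read in different sessions, a multiplicative difference between sessions (thaw, reagents, reader, operator) passes straight into the fold change. Mock subtraction removes additive background only.

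At stake is the second hypothesis in Protocol 10.1, that both regimens increase circulating HIV-specific T cells. The four within-arm magnitude outcomes carry it. Because the cells are cryopreserved, samples need not be tested as they are collected, so the exposure is avoidable.

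**Working it through.** **Inputs from the documents.** SAP 5.3, Table 4: n=8 per arm and the test "Two-Sided Exact Wilcoxon Signed-Rank Test to achieve exact p-value < 0.05". "The effect under the alternative hypothesis was a GMR of 2 on the raw T-cell response measures", so the mean log difference is ln 2 = 0.693. "An SD of 0.8 for both pre- and post-vaccination measurements was assumed to calculate power", on the natural-log scale, with r between 0.8 and 0.9. SAP 4.1.8: "Type-I error control (alpha) for all comparisons will be set to 0.05, and all tests will be two-sided".

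**Assumed, because the documents give no figure.** Either a shift common to all pre/post pairs of 1.1- to 1.5-fold, or a per-run log SD s of 0.2 to 0.3. Each result below uses 200,000 simulated datasets unless stated otherwise.

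**1. The plan's own power.** SD of the paired difference = 0.8 × √(2(1−r)) = 0.506 (r=0.8) or 0.358 (r=0.9). The exact null is enumerated over 2⁸ = 256 sign patterns. The test rejects at W ≤ 3 or W ≥ 33, so its attainable size is 10/256 = 3.9%. Power is 86.7% (r=0.8) and 99.0% (r=0.9), which agrees with SAP Table 4 (>80% and >95%). Protocol 10.7.4.2 gives 87% for r=0.9 and >95% for r=0.8. Those labels are reversed relative to the SAP and to this calculation, which is a separate point.

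**2. Independent run effects.** The variance becomes SD² + s²(1 + 1/k), where k is the number of baseline runs averaged. For example, with r=0.8, s=0.2, k=1: √(0.256 + 0.080) = 0.580.

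| s | k | Power, r=0.8 | Power, r=0.9 |
|---|---|---|---|
| 0 | – | 87% | 99% |
| 0.2 | 1 | 77% | 92% |
| 0.2 | 3 | 80% | 95% |
| 0.3 | 1 | 65% | 80% |
| 0.3 | 3 | 72% | 88% |

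With no vaccine effect, rejection stays at about 3.9% in every row. If the data behind r already include between-run noise, this power loss is already in the plan's figure.

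**3. A shift common to all pairs, with no vaccine effect.** Differences are Normal(ln f, SD).

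| Shift f | False positives, r=0.8 | r=0.9 |
|---|---|---|
| 1.0 | 3.9% | 4.0% |
| 1.1 | 6.0% | 8.0% |
| 1.2 | 11.6% | 19.8% |
| 1.25 | 15.7% | 27.9% |
| 1.5 | 43.0% | 71.8% |

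If instead all baselines share one run and all post-boost samples another, with s=0.2 per run, the rates are 21.4% and 32.9%.

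**4. The 20 SFU floor.** SAP 8.3.B sets non-reactive results to 20 SFU, and zero changes are dropped from the test. With 7 non-zero pairs the 1.2-fold rates hardly move (11.8% and 19.4%). With 6, the attainable size is 2/64 = 3.1% and the rates fall to 7.2% and 11.3% (24.1% and 43.8% at 1.5-fold). With 5, the smallest p is 2/32 = 0.0625, so the test cannot reject.

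**5. Between arms.** Adding one constant to every log fold change in both arms leaves the ranks unchanged. A simulation of 4,000 datasets with a common 1.5-fold shift (r=0.9) gave 5.5%, where the simulation error is √(0.05 × 0.95/4000) = 0.3 points.

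**6. Same-session testing.** A multiplicative session effect cancels from the ratio, which restores step 1: size 3.9%, power 86.7% or 99.0%.

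**7. Can the placebo arm reveal drift?** With two participants and r=0.9, the 95% t-interval for the GMR is a factor of exp(12.71 × 0.358/√2) ≈ 25 either way.

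**The case against.** The strongest reply is that inflation needs alignment. Participants start at no more than two per week, and the documents do not describe batching, so a common shift is not the default. That stands. A reader might infer that any run-to-run shift would pass for a vaccine effect in these tests. The documents do not support this: step 2 shows that independent run effects leave the false-positive rate alone. Alignment is possible under SAP 10.2 but not established.

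A reader might also infer that the trial has no concurrent control. It has two randomised placebo participants, and Protocol 4.2 pools them with three from the earlier M&M trial. The gap is in the within-arm tests, which use none of them. Two are too few to estimate drift, and the other three are not concurrent.

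The safeguards are real: different days are allowed only if QC is met, and the SAP has replicate mock wells, a PHA control, standardised reader settings, external proficiency testing and laboratory blinding. They limit gross failures. None is stated to bound or remove a moderate multiplicative shift between passing runs.

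It is tempting to subtract the Env and Nef/Acc fold change as a correction. The documents argue against it. Protocol 4.2 expects vaccination to move targeting away from variable epitopes, so a genuine fall in Env or Nef responses would be counted as a rise in the vaccine pools. A pool at the floor at both visits shows no shift at all. These pools share the plate and cells with the vaccine pools, not the wells.

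Finally, a modest artefact would rarely look like the planned effect. Under a 1.2-fold shift the chance of an observed GMR of 2 or more is 0.2% or less, and under 1.5-fold it is 5.4% (r=0.8) or 1.1% (r=0.9). This protects readers who weigh effect size, as Protocol 10.7.1 asks. It does not protect the p-value.

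**Conclusion.** The point holds in limited form. The plan permits split-session testing of a participant's paired samples, and the within-arm magnitude tests have no means of separating an aligned session shift from a vaccine effect. The false-positive range of 6%-43% (r=0.8) or 8%-72% (r=0.9) applies only under an assumed common shift of 1.1- to 1.5-fold with eight non-zero pairs. It is lower if two or more floored pairs drop out. The power loss applies only if run noise lies outside the assumed r, and averaging baseline runs softens it. Between-arm Outcomes 1.2, 1.4, 1.6 and 1.8 are largely protected. Nothing here shows that drift occurred. It is worth changing because stored cells make the remedy simple where assays are still to be run.

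**What to change.** **Assays not yet run (SAP 10.2).** Replace the different-days allowance with a requirement that each participant's baseline, D35, D42 and D56 cryopreserved samples be thawed and run in one session. Where that is impossible, put a stored baseline aliquot, for example from the baseline leukapheresis, into every session and compute the fold change within session. The cost is waiting for the D56 sample and using some baseline cells, which matters because SAP 8.3.A recognises that cells can run short. No visits are added.

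**Assays already run.** SAP 10.1 is partly in the past tense, so some testing may be complete and not repeatable. Record the run date and session of every result, state how samples were batched, and repeat Outcomes 1.1, 1.3, 1.5 and 1.7 on same-session pairs only, as a sensitivity analysis. With five or fewer non-zero pairs the exact test cannot reach p<0.05, so the result should then be described, not tested.

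**Reporting (SAP 8.3.B).** Show the placebo fold changes and the already planned Env and Nef/Acc fold changes beside each within-arm result as a descriptive check. Do not subtract them. This costs one table or figure.

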10.3 Reporting

Analysis of blinded study data and preparation of a study report for primary and secondary endpoints will be performed by UNC CFAR Biostatistician, [name] under the supervision of [name]. Data will be submitted by .xls and .pdf (QC control).

11 References

- 1. Warren, J.A., et al., *The HIV-1 latent reservoir is largely sensitive to circulating T cells.* Elife, 2020. **9**.
- 2. Xu Y, et al., *HIV-specific T cell responses are highly stable on antiretroviral therapy.* Molecular Therapy Methods and Clinical Development, 2019.
